8.4.3 Safety Analyses

Safety analyses will be performed in all treated subjects. Descriptive statistics of safety will be presented using NCI CTCAE version 4.0 by treatment group. All on-study AEs, treatment-related AEs, SAEs, and treatment-related SAEs will be tabulated using worst grade per NCI CTCAE v 4.0 criteria by system organ class and preferred term. On-study lab parameters including

hematology, chemistry, liver function, and renal function will be summarized using worst grade NCI CTCAE v 4.0 criteria.

8.4.4 Pharmacokinetic Analyses

The concentration vs. time data obtained in this study may be combined with data from other studies in the clinical development program to develop population PK models. These models may be used to evaluate the effects of intrinsic and extrinsic covariates on the PK of nivolumab and to determine measures of individual exposure (such as steady state peak, trough and time averaged concentration). Model determined exposures may be used for exposure response analyses of selected efficacy and safety endpoints. If the analyses are conducted, the results of population PK and exposure response analyses will be reported separately.

8.4.5 Biomarker Analyses

To evaluate PD-L1 status as a predictive biomarker, a Cox proportional hazards model will be used to test the interaction between PD-L1 status (positive vs negative) and treatment arm for the OS and DFS endpoints. Additionally, OS and DFS will be analyzed within each PD-L1 expression subgroup (positive and negative) including log-rank tests and HRs with corresponding CIs. OS and DFS curves and medians will be estimated using KM methodology. These analyses will be descriptive and not adjusted for multiplicity.

Methodology for further exploratory biomarker analyses will be described in the SAP.

8.4.6 Outcomes Research Analyses

The analysis of EQ-5D and FACT-E (including FACT-G, FACT-G7, and ECS) data will be performed in all randomized subjects who have an assessment at baseline (Day 1, assessment prior to administration of drug on day of first dose) and at least 1 subsequent assessment while on treatment. Questionnaire completion rate, defined as the proportion of questionnaires actually received out of the expected number, will be calculated and summarized at each assessment point.

- EQ-5D data will be described by treatment group as randomized in the following ways:
- EQ-5D index scores will be summarized at each assessment time point using descriptive statistics (ie, N, mean with SD and 95% CI, median, first and third quartiles, minimum, maximum). The UK scoring algorithm will be applied as a reference case.
- EQ-VAS scores will be summarized at each assessment time point using descriptive statistics (ie, N, mean with SD and 95% CI, median, first and third quartiles, minimum, maximum).
- The proportion (N) of subjects reporting no, moderate, or extreme problems will be presented for each of the 5 EQ-5D dimensions at each assessment time point. Subjects with missing data will be excluded from the analysis.
- A by-subject listing of the level of problems in each dimension, corresponding EQ-5D health state (ie, 5-digit vector), EQ-5D index score, and EQ-VAS score will be provided.

From the beginning of the on-treatment phase through follow-up visit 2, data for the FACT-E will be described by assigned treatment group in the following ways:

- ECS, FACT-G7, FACT-G, and FACT-E total scores will be summarized at each assessment time point using descriptive statistics (ie, N, mean with SD and 95% CI, median, first and third quartiles, minimum, maximum).
- Changes from baseline in ECS, FACT-G7, FACT-G, FACT-E total scores will be summarized at each post-baseline assessment time point using descriptive statistics (ie, N, mean with SD and 95% CI, median, first and third quartiles, minimum, maximum).

During the survival follow-up phase, data for the ECS and FACT-G7 will be described by assigned treatment group in the following ways:

[figure not shown]
- ECS and FACT-G7 scores will be summarized at each assessment time point using descriptive statistics (ie, N, mean with SD and 95% CI, median, first and third quartiles, minimum, maximum).
- Changes from baseline in ECS and FACT-G7 scores will be summarized at each post-baseline assessment time point using descriptive statistics (ie, N, mean with SD and 95% CI, median, first and third quartiles, minimum, maximum).

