4.5 Selection and Timing of Dose for Each Subject

Table 4.5-1: Nivolumab (or placebo) dosing

Drug	Dose	Frequency of administration	Route of administration	Duration
Nivolumab (or placebo)	240 mg (or placebo) [Cycles 1-8]	Every 2 weeks, for 8 doses	Intravenous (IV) infusion	Until recurrence or discontinuation from study for a maximum of 1 year
	480 mg (or placebo) [Cycles 9-17]	Every 4 weeks starting at Cycle 9		

Subjects will receive treatment with nivolumab (BMS-936558) or placebo monotherapy. Subjects randomized to nivolumab will receive 240 mg nivolumab administered as an IV infusion over 30 minutes every 2 weeks for 16 weeks (8 doses) followed by 480 mg nivolumab administered as an IV infusion over 30 minutes every 4 weeks beginning at Week 17 (2 weeks after the 8th dose). Subjects randomized to placebo will receive placebo administered as an IV infusion over 30 minutes every 2 weeks for 16 weeks (8 doses) followed by placebo as an IV infusion over 30 minutes every 4 weeks beginning at Week 17 (2 weeks after the 8th dose). Treatment will be given until disease recurrence, unacceptable toxicity, or subject withdrawal of consent with a maximum of 1-year total duration of study medication.

First dose must be administered within 3 calendar days following randomization. There are no pre-medications recommended on the first cycle. If an acute infusion reaction is noted, subjects should be managed according to [Section 4.5.6](#). At the end of the infusion, flush the line with a sufficient quantity of diluent. Refer to drug preparation manual for more detail.

Dosing modifications:

There will be no dose modifications allowed for the management of toxicities of individual subjects. Subjects should be carefully monitored for infusion reactions during nivolumab administration. If an acute infusion reaction is noted, subjects should be managed according to [Section 4.5.6](#).

Doses of nivolumab may be interrupted, delayed, or discontinued depending on how well the subject tolerates the treatment. Dosing visits are not skipped, only delayed.

Dosing window:

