Prior to re-initiating treatment in a subject with a dosing delay lasting > 6 weeks (42 days) from the last dose of nivolumab (or placebo) during Cycles 1-8 or > 10 weeks (70 days) from the last dose of nivolumab (or placebo) during Cycles 9-17, the BMS medical monitor must be consulted. Tumor assessments should continue as per protocol even if dosing is delayed. Periodic study visits to assess safety and laboratory studies should also continue every 6 weeks or more frequently if clinically indicated during such dosing delays.

- Any adverse event, laboratory abnormality, or under current illness which, in the judgment of the Investigator, presents a substantial clinical risk to the subject with continued nivolumab dosing.

Post treatment study follow-up is critically important and is essential to preserving subject safety and the integrity of the study. Subjects who discontinue study treatment will continue to be followed for collection of tumor surveillance assessments, safety, QoL questionnaires and biomarker sampling as per protocol.

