Pregnancy Test (WOCBP only)	X	See Note	Serum or urine within 24 hours prior to the initial administration of study drug, then every 4 weeks (\pm 1 week) regardless of dosing schedule
PK and Immunogenicity Assessments			
PK samples			
Immunogenicity blood sample			

Table 5.1-2: On-Treatment Procedural Outline (CA209577)

Procedure	Cycle 1 Day 1 (C1D1)	Each cycle on Day 1 (up to 2 days prior to dosing, unless indicated otherwise in the Notes)	Notes Each cycle duration is 2 weeks until 8 doses of nivo/placebo are complete. Remaining subsequent cycles are 4 weeks in duration Treatment is until recurrence or discontinuation from study for maximum treatment duration of 1 year		
Efficacy Assessments					
Tumor Imaging Assessment		See Section 5.4 . Every 12 weeks (\pm 7 days) from first dose of study treatment through 12 months or distant recurrence whichever comes first			
Exploratory Biomarker Assessments					
Outcomes Research Assessments					
FACT-E	X	See Note	Assessed following drug vial assignment and preferably prior to procedures at Cycles 1, 3, 5, 7, 9, 10, 11, 12, 13, 14, 15, 16, and 17 (\pm 2 days).		
EQ-5D	X	See Note			
Health Care Resource Utilization	X	See Note			
Study Drug					
IWRS Drug Vial Assignment	X	X	Vials may be assigned up to 3 days prior to first dose date		

Table 5.1-2: On-Treatment Procedural Outline (CA209577)

Procedure	Cycle 1 Day 1 (C1D1)	Each cycle on Day 1 (up to 2 days prior to dosing, unless indicated otherwise in the Notes)	Notes Each cycle duration is 2 weeks until 8 doses of nivo/placebo are complete. Remaining subsequent cycles are 4 weeks in duration Treatment is until recurrence or discontinuation from study for maximum treatment duration of 1 year
Dispense Study Treatment (Active drug or placebo - blinded)	X	X	
First dose to be administered within 3 calendar days of randomization, then every 2 weeks for 8 doses and every 4 weeks beginning at week 17 (2 weeks after the 8th dose). See Section 4.5.
 
For Cycles 1-8, subjects may have study drug administered up to 2 days before or 3 days after the scheduled dosing date. Subjects may be dosed no less than 12 days from the previous dose. For Cycles 9-17, subjects may be dosed within a +/- 3 day window.

^a TSH, Free T3, Free T4 (Total T3/T4 are acceptable if free T3/T4 are not available) should be performed prior to dosing at Cycles 1, 4, 7, 10, 12, 14, and 16

Table 5.1-3: Follow-Up Procedural Outline (CA209-577)

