Procedure	Follow-up, Visits 1 and 2 ^a FU1: 30 days (\pm 7 days) FU 2: 84 days (\pm 7 days)	Survival Follow-Up Visits ^b [REDACTED] from FU2 (\pm 14 days)	Notes
Safety Assessments			
Targeted Physical Examination	X		
Adverse Events Assessment	X		Assessed using NCI CTCAE v. 4.0. See Sections 6.1.1 and 6.2.1 .
Review of Subsequent Cancer Therapy	X	X	
Review of Concomitant Medications	X		
Laboratory Tests	X		Include CBC w/differential, LFT's, BUN or serum urea level, creatinine, Na, K, Cl, LDH, Glucose, amylase, lipase, TSH (with reflexive Free T4 and Free T3. Total T3/T4 are acceptable if free T3/T4 are not available.) Urinalysis as clinically indicated To be done at FU1. To be repeated at FU2 if study related toxicity persists.
Pregnancy Test (WOCBP only)	X		Serum or urine pregnancy testing is only required at FU1 and FU2, unless increased frequency and duration is required per local regulations.
Efficacy Assessments			
Tumor Imaging Assessment	Every 12 weeks (\pm 7 days) \leq 12 months Every 12 weeks (\pm 14 days) $>$ 12 months through 24 months After that follow local standard in the range 6-12 months between year 3 and year 5 with the last assessment at year 5. Until distant recurrence. All time points are relative to the first dose of study treatment		See Section 5.4 .

Table 5.1-3: Follow-Up Procedural Outline (CA209-577)

Procedure	Follow-up, Visits 1 and 2 ^a FU1: 30 days (\pm 7 days) FU 2: 84 days (\pm 7 days)	Survival Follow-Up Visits ^b [REDACTED] from FU2 (\pm 14 days)	Notes
Outcomes Research Assessments			
EQ-5D	X	X	Prior to any assessments at FU1 and 2. [REDACTED] (\pm 14 days) after FU2, [REDACTED] [REDACTED] up to 2 years from last dose
FACT-E	X		Prior to any assessments at FU1 and 2.
ECS		X	[REDACTED] (\pm 14 days) after FU2, [REDACTED]
FACT-G7		X	[REDACTED] up to 2 years from last dose.
Health Care Resource Utilization	X		
Exploratory Biomarker Assessments			
[REDACTED]			
Subject Status			
Survival Status	X	X	[REDACTED] (\pm 14 days) or more frequently as needed after FU2, [REDACTED] [REDACTED] to include subsequent anticancer therapy.
Progression-free survival after the next line of subsequent therapy (PFS2)	X	X	Following first progression, subjects will continue to be followed during the safety and survival follow-up visits. Timing of second progression per investigator's assessments will be documented.

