The FACT-E questionnaire and selected components, including the FACT-G7 and ECS, will be used to assess the effects of underlying disease and its treatment on health-related quality of life (HRQL). As a generic cancer-related core, the FACT-E includes the 27-item FACT-General (FACT-G) to assess symptoms and treatment-related effects impacting physical well-being (PWB; seven items), social/family well-being (SWB; seven items), emotional well-being (EWB; six items), and functional well-being (FWB; seven items). Seven of these items comprise the FACT-G7, an abbreviated version of the FACT-G that provides a rapid assessment of general HRQL in cancer patients. In addition, the FACT-E includes a 17-item disease-specific ECS that assesses concerns related to swallowing, vocalization, breathing, dry mouth, eating, disrupted sleep due to coughing, stomach pain, and weight loss. Each FACT-E item is rated on a five-point

scale ranging from 0 (not at all) to 4 (very much). Scores for the PWB, FWB, SWB, and EWB subscales can be combined to produce a FACT-G total score, which provides an overall indicant of generic HRQL, while the FACT-G and ECS scores can be combined to produce a total score for the FACT-E, which provides a composite measure of general and targeted HRQL. Higher scores indicate better HRQL. The full FACT-E will be administered to subjects during the on-treatment phase and at follow up visits 1 and 2. To minimize subject response and administrative burden, only the FACT-G7 and ECS will be administered during the survival phase after FU2 for up to 2 years after the last dose.

In addition to the aforementioned subject-reported outcomes, health care resource utilization data will be collected for all randomized subjects using an internal case report form developed for use in previous trials. The form, which is completed by study staff, records information about hospital admissions, including number of days spent in various wards and discharge diagnosis, as well as non-protocol specified visits related to study therapy, including date of visit, reason for visit, and type of visit. The health care resource utilization data will be used to support subsequent economic evaluations.

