8.2 Populations for Analyses

- All Enrolled Subjects: All subjects who signed an informed consent form and were registered into the IWRS.
- All Randomized Subjects: All subjects who were randomized to any treatment arm in the study. This is the primary dataset for analyses of study conduct, study population, and efficacy.
- All Treated Subjects: All randomized subjects who received at least one dose of nivolumab or placebo during the study. This is the primary dataset for analyses of exposure and safety.
- PK Subjects: Subjects with available serum time-concentration data from randomized subjects dosed with nivolumab.
- Outcome Research subjects: randomized subjects who have an assessment at screening/baseline and at least 1 follow-up assessment
- Immunogenicity subjects: nivolumab treated subjects who have an assessment at screening/baseline and at least 1 follow-up assessment

- Biomarker subjects: All randomized subjects with available biomarker data (PD-L1 status and other assays).

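### Protocol 8.4.6 requires an on-treatment post-baseline questionnaire that 8.2 does not, so subjects who stop after one or two doses drop out of the follow-up quality-of-life summaries

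*Protocol*

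**What the plan says.** The protocol defines the quality-of-life population twice.

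- Section 8.2 describes outcomes research subjects as "randomized subjects who have an assessment at screening/baseline and at least 1 follow-up assessment". It does not say that the later assessment must be on treatment.
- Section 8.4.6 performs the EQ-5D and FACT-E analysis in randomized subjects with a pre-dose Day 1 assessment and "at least 1 subsequent assessment while on treatment".

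Collection does not stop with treatment.

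- Table 5.1-2 schedules the on-treatment forms "preferably prior to procedures at Cycles 1, 3, 5, 7, 9, 10" and at every cycle from there to Cycle 17.
- Section 5.7 says: "The full FACT-E will be administered to subjects during the on-treatment phase and at follow up visits 1 and 2". Table 5.1-3 places EQ-5D and FACT-E "Prior to any assessments at FU1 and 2", then continues EQ-5D, ECS and FACT-G7 up to two years from the last dose.
- Section 4.5.5 says: "Subjects who discontinue study treatment will continue to be followed for collection of tumor surveillance assessments, safety, QoL questionnaires and biomarker sampling".

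Section 8.4.6 also plans to report these off-treatment data by randomized arm: FACT-E scores and changes from baseline through FU2, then ECS and FACT-G7 in survival follow-up.

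**The concern.** Two programmers, one working from 8.2 and one from 8.4.6, would build different analysis sets. The difference is not random. The subjects whom 8.4.6 removes and 8.2 keeps are those with no post-baseline form on treatment, chiefly those who stopped after one or two doses because of toxicity, relapse or withdrawal from study drug. Whether a subject is in the set then depends on something that happens after randomization and that treatment can influence.

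The filter also works against the protocol's own collection effort. A valid FU1, FU2 or survival-phase form is discarded from the summary for that visit because an earlier form, at a visit the subject did not reach on treatment, is absent. If early stoppers feel worse, the follow-up summaries look somewhat better than the randomized population did.

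**Working it through.** The plan states no sample size, power or event figure for quality of life, so there is nothing to reproduce. The check is a comparison of the two rules against the schedule, followed by an illustration of size.

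**1. First qualifying form.** Section 4.5 gives the early schedule as "Every 2 weeks, for 8 doses". Cycle 3 is therefore due on Day 1 + 14 + 14 = Day 29. There is no Cycle 2 questionnaire.

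**2. Forms available to a subject who stops before Cycle 3.** Section 3.5 puts FU1 about 30 days after the last dose and FU2 about 84 days after FU1.

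| Last dose | FU1 | FU2 | Post-baseline form on treatment |
|---|---|---|---|
| Cycle 1, Day 1 | 1 + 30 = Day 31 | 31 + 84 = Day 115 | none |
| Cycle 2, Day 15 | 15 + 30 = Day 45 | 45 + 84 = Day 129 | none |

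**3. Apply both rules.** With a Day 1 baseline and an FU1 form, either subject meets 8.2. This is so whether its follow-up assessment means any later assessment or one in the follow-up phase. Neither subject meets 8.4.6 on its plain wording.

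**4. Dose holds.** Section 4.5.2 lets dosing be delayed up to 42 days from the last dose in Cycles 1-8, and the scheduled forms are tied to cycles. A subject held after Cycle 2 and then discontinued could reach Day 15 + 42 = Day 57 with no scheduled qualifying form.

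**5. How many.** The documents give no rate of stopping before Cycle 3. For an assumed share s, n = 760 × s:

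- s = 1%: 7.6, about 8
- s = 3%: 22.8, about 23
- s = 5%: 38
- s = 10%: 76 (about 51 and 25 if split 2:1)

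These are ceilings on lost data, since not every such subject completes a later form.

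**6. A figure not to use.** SAP Table 5.1-1 assumes a DFS hazard of 0.035 per month at the start. Over 28 days, 1 − exp(−0.035 × 28/30.4375) = 0.0317, and 0.0317 × 760 = 24 subjects. The arithmetic is right, but it does not estimate the number dropped, for the reasons given under the objection.

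**7. Effect on a mean.** If a share p of those with an FU1 form is dropped, and they score d points below those kept, the reported mean rises by p × d. With p from 1% to 10% and d = 10 (both assumed), the shift is 0.1 to 1.0 points. FACT-E has 27 + 17 = 44 items scored 0 to 4, a range of 0 to 176, so this is 0.06% to 0.57% of the scale. The difference between arms moves by 10 × (p in one arm − p in the other). It is zero if the shares are equal, and 0.9 points if one arm is at 1% and the other at 10%.

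**The case against.** Several points on the other side stand.

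- **The SAP may already settle it.** Protocol 8.3.3 leaves outcomes research endpoints to the SAP, and the relevant SAP text is blacked out in the public copy. A reader might infer that the final analysis does exclude these subjects. Only the conflict within the protocol can be shown.
- **The on-treatment period is not defined for questionnaires in the visible text.** SAP 6.1 extends on-treatment evaluations to 30 or 100 days after the last dose, but names only laboratory tests and vital signs. If a similar window applied to questionnaires, FU1 (30 ± 7 days after the last dose) would often qualify and the group dropped would shrink. Nothing visible says that it applies.
- **The size cannot be taken from the DFS hazard.** A reader might infer that about 24 subjects are lost, or more once toxicity stops are added. The documents do not support this. The hazard is a smoothed planning value used up to one year in controls. Subjects are disease-free on imaging within 4 weeks before randomization, and the first scheduled scan is at 12 weeks. Deaths before Day 29 leave no later form to drop.
- **Bias between arms is not shown.** A reader might infer that the filter flatters nivolumab, because toxicity stops are more likely there. That is plausible, but the documents give no early stopping rate by arm, and the assumed DFS hazard is the same in both arms for the first 3 months.
- **Quality of life is exploratory**, summarized descriptively with no planned test in 8.4.6.

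These points limit the consequence. They do not remove the conflict between the two sections, and neither 5.7 nor 8.4.6 gives a reason for the on-treatment condition.

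**Conclusion.** The concern holds as a conflict between two stated populations, with an avoidable selection on a post-randomization event in 8.4.6. It reaches only subjects with no post-baseline form on treatment. By schedule these are mainly subjects who stop before Cycle 3; those who stop later and have completed an on-treatment form stay in.

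The number affected cannot be derived from the documents. About 8 to 76 of 760 follows from an assumed 1% to 10% stopping before Cycle 3, and would be lower if a post-dose window counts FU1 as on treatment. The effect on means is probably small: up to about 1 point on FACT-E under the assumptions shown. A difference between arms is possible but not demonstrated. DFS and OS are unaffected. The correction is still worth making, because the data are already collected and the summaries that lose them are ones the protocol plans to report.

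**What to change.** Use one definition in Protocol 8.2, Protocol 8.4.6 and the SAP: randomized subjects with a baseline assessment and at least one post-baseline assessment, on or off treatment (FU1, FU2 and survival follow-up included).

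Reconcile the baseline wording at the same time. Section 8.2 accepts a screening or baseline assessment, while 8.4.6 requires one on Day 1 before dosing. Changing only the on-treatment phrase would leave the two sections different.

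Confirm the wording against the unredacted SAP first. If the SAP already uses this definition, only the protocol text needs aligning.

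The cost is small: no new visits, data or sample size. It is, however, a late change. The rationale for Revised Protocol 04 says that the first planned interim analysis is complete, so the change should be dated and labelled as such, with the approval that Section 9.1.1 requires. The new definition still requires one assessment after randomization, so some selection remains, but it no longer discards forms that were completed.

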1.3.3 Exploratory Objectives

- To assess the overall safety and tolerability of nivolumab versus placebo in subjects with resected EC or GEJ cancer.
- To evaluate the distant metastasis free survival (DMFS) in subject with resected EC or GEJ cancer.
- To evaluate whether PD-L1 status is a predictive biomarker for DFS and OS in subjects with resected EC or GEJ cancer.
- To evaluate PD-L1 status prior to CRT and at the time of surgery in subjects with resected EC or GEJ cancer.
- To explore potential biomarkers associated with clinical efficacy (DFS, and OS) and/or incidence of adverse events of nivolumab by analyzing biomarker measures within the tumor microenvironment and periphery [REDACTED] in comparison to clinical outcomes.
- [REDACTED]
- [REDACTED]
- To characterize the pharmacokinetics (PK) and explore exposure-response relationships with respect to safety and efficacy.
- To characterize the immunogenicity of nivolumab.

- To assess the subject's overall health status using the 3-level version of the EQ-5D (EQ-5D-3L) index and visual analog scale.
- To assess the subject's cancer-related quality of life using the Functional Assessment of Cancer Therapy-Esophageal (FACT-E) questionnaire and selected components, including the Esophageal Cancer Subscale (ECS) and 7-item version of the FACT-General (FACT-G7).
- To assess progression-free survival after the next line of the subsequent therapy (PFS2) as assessed by investigators.

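### Protocol 8.4.6 plans no change from baseline and no between-arm estimate for EQ-5D index and EQ-VAS, although every analysed subject must have a baseline score; a baseline-adjusted descriptive contrast would be more precise

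*Protocol*

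**What the plan says.** The objective in Protocol Section 1.3.3 is exploratory: "To assess the subject's overall health status using the 3-level version of the EQ-5D (EQ-5D-3L) index and visual analog scale".

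Entry to the questionnaire analysis in Protocol Section 8.4.6 is conditional on completed forms. Each person counted must "have an assessment at baseline (Day 1, assessment prior to administration of drug on day of first dose) and at least 1 subsequent assessment", the later form falling within the treatment period. The section continues: "EQ-5D data will be described by treatment group as randomized in the following ways". For the index, "EQ-5D index scores will be summarized at each assessment time point using descriptive statistics"; the visual analog scale has the same rule, "EQ-VAS scores will be summarized at each assessment time point using descriptive statistics". The listed statistics are N, mean with SD and 95% CI, median, quartiles and range. Proportions per EQ-5D dimension, a by-subject listing and a completion rate at each assessment point are also planned ("Questionnaire completion rate, defined as the proportion of questionnaires actually received out of the expected number").

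The FACT family gets one thing more: "Changes from baseline in ECS, FACT-G7, FACT-G, FACT-E total scores will be summarized at each post-baseline assessment time point". The same is planned for ECS and FACT-G7 in survival follow-up. There is no matching item for EQ-5D, and no between-arm difference or longitudinal model for any instrument.

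Protocol Section 3.5 makes recurrence a reason to stop study drug. Section 4.5.5, Table 5.1-3 and Section 5.7 keep questionnaires going afterwards, with EQ-5D at FU1, FU2 and survival visits up to 2 years from last dose. Protocol Section 8.3.3 leaves outcomes-research endpoints to the SAP. The SAP's questionnaire text (after Section 4.1.3) is redacted after its first sentence.

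**The concern.** In a blinded, placebo-controlled adjuvant trial, health status will be read as nivolumab against placebo. Under the readable rule, a reader must compare two separate confidence intervals at each visit. The baseline score, usually the strongest single predictor of a later score, decides who enters the analysis and fills its own row in the table, but is not otherwise used for EQ-5D.

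The on-treatment series also thins out selectively. A subject whose disease recurs moves to the follow-up visits, so the late on-treatment means describe those still recurrence-free. If these subjects were healthier at baseline, the means rise without anyone improving.

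The stake is limited to the precision and interpretation of an exploratory outcome. No alpha, power statement or decision depends on it.

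**Working it through.** **Inputs from the documents.** 760 subjects at 2:1, about 507 and 253 (SAP 5.3). DFS hazards from SAP Table 5.1-1: 0.035 per month on placebo throughout the first year; on nivolumab 0.035 to month 3, then 0.035 × 0.667. EQ-5D is collected at 13 on-treatment visits, Cycle 1 to Cycle 17 (Protocol Table 5.1-2).

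**Assumed, not in the documents.** Baseline-to-later correlation rho of 0.4 to 0.7. Log-hazard slope b of 0.2 to 0.4 per SD of better baseline health. EQ-VAS SD of 20 points. A deficit D of 5 to 15 points after recurrence.

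**1. The plan's own figures.** The documents give no SD, effect size or power for EQ-5D. The nearest figures are the 1-year DFS rates:
- placebo exp(−0.035 × 12) = 65.7%
- nivolumab exp(−0.035 × 3 − 0.035 × 0.667 × 9) = 73.0%

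Both match Table 5.1-1.

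**2. Precision.** Relative to the raw later score, the variance of the arm difference is 1 − rho² with baseline as covariate and 2(1 − rho) for plain change from baseline.

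| rho | covariate | cut | equivalent sample | change score |
|---|---|---|---|---|
| 0.4 | 0.84 | 16% | 1/0.84 = 1.19 | 1.20 |
| 0.5 | 0.75 | 25% | 1/0.75 = 1.33 | 1.00 |
| 0.7 | 0.51 | 49% | 1/0.51 = 1.96 | 0.60 |

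With all 760 subjects, the raw SE is √(1/507 + 1/253) = 0.077 SD, or 1.54 points at SD 20. With baseline as covariate it is 1.41, 1.33 or 1.10 points. A bare change score is less precise than the raw score when rho is below 0.5, so copying the FACT rule to EQ-5D would not by itself deliver the gain.

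**3. Who remains at Cycle 17.** Cycle 9 falls 16 weeks after first dose, and Cycle 17 eight 4-week cycles later, at 48 weeks = 336 days = 11.04 months.
- Placebo event-free: exp(−0.035 × 11.04) = 0.680, so 32% have had an event.
- Nivolumab event-free: exp(−0.105 − 0.035 × 0.667 × 8.04) = 0.746, so 25% have had an event.

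**4. Selection on baseline health.** With hazard proportional to exp(−b z), where z is the standardized baseline score, the mean z among those remaining is roughly b × (−ln S). The later mean drifts by rho times that. Here −ln S is 0.386 (placebo) and 0.293 (nivolumab).
- Placebo: 0.5 × 0.2 × 0.386 = 0.039 up to 0.7 × 0.4 × 0.386 = 0.108 SD. Numerical integration gives 0.038 to 0.105.
- Nivolumab: 0.029 to 0.082 SD. Numerical integration gives 0.029 to 0.080.
- Arm difference: shifted against nivolumab by 0.009 to 0.025 SD.

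For scale, about 172 placebo and 378 nivolumab subjects remain, so the SE of a raw difference is √(1/172 + 1/378) = 0.092 SD. The shift is 0.1 to 0.3 of one SE.

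**5. Worsening after recurrence.** If subjects with recurrence score D points lower and drop out of the visit mean, the arm difference at one year is understated by (0.343 − 0.270) × D = 0.073 × D, or 0.4 to 1.1 points. In a simulation (1,000 runs; rho 0.5, SD 20, recurrence mildly related to baseline), the gap between the full-population and observed differences was 0.55, 0.97 and 1.32 points at D = 5, 10 and 15. After baseline adjustment it was 0.35, 0.79 and 1.09. Adjustment removed about 0.2 points each time, the part due to baseline selection, and left roughly 0.073 × D.

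**The case against.** The strongest reply is that the plan does what its objective asks. The EQ-5D objective is exploratory and worded as an assessment, whereas the DFS and OS objectives are worded as comparisons, and 8.4.6 promises a description by arm. That stands: the lack of a contrast is a limitation and not a contradiction.

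A reader might go further and infer that EQ-5D will be analysed only as raw means. The documents do not support this. Medians, quartiles, confidence intervals, dimension proportions and completion rates are planned as well, and the redacted SAP text may contain change scores or a model. Against that, 8.4.6 is itself readable and, unlike 8.4.5 and 8.4.7, does not send the reader to the SAP for further method. The finding therefore holds for the protocol text.

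A reader might also infer that subjects drop out of EQ-5D at recurrence. They do not. They leave the on-treatment series, and their forms continue at FU1, FU2 and survival visits. N and completion rate at each point make the shrinking denominator visible.

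Finally, the correlations and slopes above have no source in the documents, and DFS events include deaths, for which no later score exists. Both points stand. The direction of the precision gain holds for any non-zero correlation; its size is uncertain.

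**Conclusion.** The point holds as a minor, low-cost improvement to the protocol's readable text. EQ-5D index and EQ-VAS get neither change from baseline nor a between-arm estimate there, although a baseline score is a condition of entering the analysis.

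The main loss is precision for any nivolumab-versus-placebo reading: 16% to 49% of the variance at an assumed correlation of 0.4 to 0.7. Selection into the late on-treatment visits is secondary, about 0.01 to 0.03 SD between arms under assumed slopes. It would be wrong to conclude that baseline adjustment cures the effect of recurrence: it corrects selection on baseline health but does not recover worsening after recurrence. Nothing here touches DFS, OS or error control.

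**What to change.** In Protocol 8.4.6, keep the descriptive tables. For EQ-5D index and EQ-VAS, and likewise for ECS, FACT-G7 and FACT-E total, add a mixed model for repeated measures over the scheduled on-treatment visits. Terms: baseline score, baseline-by-time, arm, time, arm-by-time, and the three randomization factors (PD-L1 status, nodal status, histology). Report the adjusted nivolumab-minus-placebo difference with 95% CI at each visit, labelled descriptive.

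Include follow-up forms only after assigning them to time since randomization. FU1 is 30 days after last dose, so it falls near day 31 for a subject who stops after Cycle 1 and near day 367 for one who completes Cycle 17 on schedule (337 + 30). These cannot share a visit label. State that the on-treatment model describes subjects still on the visit series and rests on a missing-at-random assumption.

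The cost is some analysis wording and one extra model on data already collected, with no new forms and no alpha spent. If the redacted SAP section already contains such a model, aligning 8.4.6 with it is enough.
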